## **Development and validation of a health behaviour theory-based questionnaire to explore the willingness of older adults and informal caregivers to deprescribe (HBQtD)**

### *Method for data collection*

The questionnaire begins with a short introduction covering the importance of the study, its objectives, anonymity and the non-obligation to participate in the study and withdraw if desired. Consent will be signed before starting to fill in the questionnaire. The questionnaire initially asks 3 questions to determine participant eligibility, and the initial draft of the questionnaire consists of 3 main parts:

1. First section with questions relating to the socio-demographic and clinical characteristics of the participants. There are 5 basic demographic questions related to age, sex, education, relationship status, residence (at home, NH, ...). Three additional questions are included in this section to: (1) assess how the person feels about his or her health or that of the care recipient, on a Likert scale ranging from 1 “Poor” to 5 “Excellent”; (2) to know how many different medications (including those not prescribed by the doctor) the older person/care recipient takes per day; (3) to know if the person or the care recipient has ever tried, in the past, to reduce or stop some of the drugs in their usual treatment; (4) to know if the person/ informal caregiver are willing to deprescribe; (5) to know if the person/ care recipient is currently in the process of deprescribing at least one of the medication he or she is currently taking.
2. Second section with 58 questions for older adult questionnaire version and 55 questions for the informal caregiver version on factors that may be potential obstacles or facilitators to deprescribing behavior. Each item is rate on a Likert scale going from 1 “strongly disagree” to 5 “strongly agree”.

### [9.2. Third section with 3 open-ended questions for participants to comment on the questionnaire format, factors that have not been addressed and items that may not be relevant. An additional question is added to this first draft to identify participants interested in participating in the FG. Description of the population](#)

#### *Older Adult population*

- Be at least 60 years old : different ways of defining the older people exist, but in statistical terms, the older people are often classified above a certain age threshold (European Commission. Statistical Office of the European Union., 2020). For the purposes of this study, we adopt the definition given by the United Nations in its report called *World Population Ageing 2019: Highlights* (s. d.), that older people are those aged 60 or 65 years or older.

- Take 5 or more medications daily: the ageing process is often accompanied by an increasing burden of chronic illness, and consequently by chronic medication use that can lead to polypharmacy, defined as taking 5 or more medications (Nordin Olsson et al., 2011). In turn, polypharmacy can be considered as the most obvious sign of risks in medication treatment (Nordin Olsson et al., 2011), and potentially inappropriate medication (PIM) that include medication and medication combination, should be avoided in this population due the higher risk of causing more harm than benefit for the user, in particular, an increase mortality (Muhlack et al., 2017).

#### *Informal caregivers*

## Development and validation of a health behaviour theory-based questionnaire to explore the willingness of older adults and informal caregivers to deprescribe (HBQtD)

- Spouse, family member or closer friend: in this study informal caregiver refers to a family member, a friend that provide care or support to a dependent older person with physical or cognitive functions declines. The relationship between the informal caregiver and the care recipient is based on solidarity, and so *“based on mutual help and moral obligation within families and social networks. Informal caregivers’ work can be unpaid or remunerated”* in some way” (Abouzaid et al., 2014). Therefore, in this study those who provided informal care are: (a) working-age adults who care for older parents with disabilities, family members, neighbors or friends; (b) people of retirement age or older who care for their partner, family members, neighbors or friends

In addition, the role of the informal caregiver may vary depending on the older person's disability, but also according to their own characteristics. However, in the ambulatory setting, medication management has been identified as one of the most important informal caregivers’ role, and good medication management *“contributes to improve health outcomes and reduce institutionalizations for the care recipient”* (Gillespie et al., 2014). As a result, informal caregivers should be involved in the deprescribing decision and process (E. Reeve et al., 2016).

### Number of participants expected

Healthcare professionals	n=8			
	Questionnaire self-administration: 2 geriatricians, 2 GP, 2 pharmacists, and 2 nurses			
Older Adults	n=345			
	Cognitive pre-test: n=5	Questionnaire self-administration: n=10	Pre-test: n= 30	Validation: n=300
Informal caregivers	n=345			
	Cognitive pre-test: n=5	Questionnaire self-administration: n=10	Pre-test: n= 30	Validation: n=300

### 9.3. [Strategies for recruiting participants](#)

#### Health care professionals

For the recruitment of healthcare professionals, several organizations will be contacted, more specifically:

- General practitioners: « Centre académique de médecine général » - CAMG; ASBL « Collège de Médecine Générale de Belgique francophone » ;
- Specialist physician: Belgian Young geriatricians – BYG and the Belgian Society of gerontology and geriatrics – BSGG;
- Pharmacists: “Centre académique de soins pharmaceutiques » - CASP and the Belgian pharmaceutical association – APB

## **Development and validation of a health behaviour theory-based questionnaire to explore the willingness of older adults and informal caregivers to deprescribe (HBQtD)**

- Nurses: convenience recruitment through contact with a number of nursing home and homecare associations.

Different recruitment channels are envisaged to ensure that the healthcare professionals who will be recruited have no relationship with the researcher and/or the sponsor of this study.

### Older adults

Initially, convenience recruitment will be carried out for the “cognitive pre-test”, and for the questionnaire self-administration and FG. The French-speaking federation of patient and family associations- LUSS, and ASBL “Aidants proches”, will be contacted to help recruit participants. Then, older adults in ambulatory setting will be recruited through community pharmacies and GP. Contacts will be made with a large number of community pharmacies and also with GP in private practice and in "Maison Médicale" practices, in Brussels and Wallonia. Eligible patients will receive from pharmacists and GPs an envelope containing the information form, consent form and questionnaire, as well as a stamped envelope for returning the questionnaire and signed consent form.

In addition, day centers for older adults will be contacted, as well as organizations and social-health services and “Résidence Service”. For Brussels, Iriscare provides a list of available day centers, and senior.irisnet provides a list of homecare organizations. For Wallonia, AVIC provides a list of day centers to contact, as well as a list with homecare organizations. For the older adults who are eligible and agree to participate, a member of staff or the researcher will inform residents about the study, request the signature of informed consent and, if necessary, help in completing the questionnaire. For participants who are unable to take part, their informal caregivers will be asked if they are willing to participate (informal caregiver version of the questionnaire).

For the NH participants, a convenience sample of NH, in Brussels and Wallonia, will be contacted for participation. As for the day-care centers, the researcher or a NH staff member will inform residents about the study, request the assignment of consent and, if necessary, help in completing the questionnaire.

### Informal Caregivers:

As with the recruitment of seniors, LUSS and ASBL “Aidants proches” will be contacted to help recruit participants. Pharmacists and GPs will also be informed of the informal caregiver version of the questionnaire, and if eligible, will give to the caregiver an envelope with information form, the consent form, and the questionnaire (informal caregiver version) together with a stamped envelope to return the questionnaire and the signed consent form.

For residents in NH, or in a day-care center, or for those at home but unable to fill in the questionnaire and who have a close caregiver, the staff member of the different teams will provide the information and give all the necessary documents, as well as the questionnaire, to the close caregivers who agree to take part in the study.

## 9.4. Inclusion criteria

Older adult participants will be eligible for this study if they satisfied the following criteria:

- Age 60 years or older;
- Taking at least 5 medications daily;
- Having at least one chronic condition.

Informal caregiver participants will be eligible for this study if:

## **Development and validation of a health behaviour theory-based questionnaire to explore the willingness of older adults and informal caregivers to deprescribe (HBQtD)**

- They self-identified as a caregiver (defined as having any role in a family member or friend's management of health and/ or medication management) of an older adult who has 60 years old or older, that are taking at least 5 medications daily;
- The care recipient lived in the community (at home with or without the caregiver) or in a NH.

### 9.5. Exclusion criteria

Older adult participants will be excluded from this study if they meet any of the following criteria:

- Suffering from psychiatric trouble;
- Past or present drug or alcohol dependency;
- Having a terminal illness;
- Inability to complete a written questionnaire in French due to a functional or cognitive impairment;
- Inability to understand and express oneself in French.

Informal caregiver participant will be excluded from this study if they meet any of the following criteria:

- Caregiver age under 18 years old;
- Caregivers who are paid for the care they provide;
- Caregiver inability to give consent and complete a written questionnaire in French;
- Caregiver inability to understand and speak in French.

### 9.6. Withdrawal

Not applicable

### 9.7. Protocol Deviations

Any significant deviations from the study inclusion or exclusion criteria, study conduct, patient management or evaluation will be described and justified in the final report and communicated to the Ethics Committee, as appropriate.

### 9.8. Data Management Responsibilities

The questionnaire for the older adults will be either a paper version for self-administration, or completed with the help of the researcher or a member of the NH or day-care center staff. However, considering the growing development of IT tools for all age categories, and despite the fact that the older people are slower in adopting new technologies compared with the young, there is a proportion of this population that uses new information and communication technologies (Yap et al., 2022). So, a questionnaire will also be available online, and distributed through older adults' association above for recruitment purposes, and personal or professional networks, in Belgium.

The questionnaire for informal caregivers will also have both a paper and an online version, distributed by the caregiver associations and also by personal or professional networks, in Belgium.

## **Development and validation of a health behaviour theory-based questionnaire to explore the willingness of older adults and informal caregivers to deprescribe (HBQtD)**

Both versions of the questionnaire will be distributed using Qualtrics (UCL license) - a cloud-based platform for creating and distributing web-based surveys.

### 9.9. Data breach

Before taking part in this study, participants will be informed how, by whom and for which purpose they are being asked to be involved. This information will be given in writing in an information sheet together with the consent form (Appendix).

#### *Qualitative methodology*

For the first qualitative phase of the questionnaire's development, anonymity of all participants (healthcare professionals, older adults and informal caregivers) will be ensured by assigning an identifier code when analyzing comments from the questionnaire's self-administration and when transcribing and analyzing the FG. Also, to ensure that participants are not identified, but to be able to re-contact them, in particular for FG planning, any information likely to reveal the identity of participants (names) will be put in a separate document, secured by a password and stored offline on the hard. The questionnaires' comments and transcribed FG will also be stored offline and password-protected for 20 years at the 'Service des Archives' from the UCLouvain.. This procedure will be also explained to the participants, written and orally.

#### *Quantitative methodology*

In the quantitative phase of questionnaire validation (older adult and caregiver version), participants (older adults and informal caregivers) will be informed in writing, via an information sheet attached to the consent form, of how, by whom and for what purpose they are being asked to participate. In addition, in specific settings: ambulatory setting – day-care and home care and in NH setting, the information will also be communicated orally to the older adults, together with the information sheet and the consent form. It will be explained orally and in writing that participants will be free to choose whether or not to take part in the study, with no implications for the quality of care they receive, or for the relationship between patient/informal caregiver and healthcare professional. They will also be free to withdraw from the study at any time without justification.

For those who agree to participate, anonymity will be ensured by the allocation of an identifier code. All information likely to identify participants, such as name, date of birth or address, will not be requested. In this study, general information, such as age category, gender, place of residence (at home, accompanied or alone, in a NH), marital status and level of education will be requested.

In this study, participants will not be asked about sensitive information concerning the health of the older adult, or about information contained in patient records (e.g. biometric data, hospital information, medical photographs, biological traits, genetical material, among other sensitive information), and no patient records will be consulted. Other types of sensitive information, such as those revealing racial or ethnic origin, political opinions, religious or philosophical beliefs, trade-union membership, sexual orientation or activity will not be investigated. This study will focus on questions relating to the number of medications taken by the person or care recipient, as well as their perception of their (or the care recipient's) health status, medication deprescription and medication intake. All the data to be collected are based on a theoretical

## **Development and validation of a health behaviour theory-based questionnaire to explore the willingness of older adults and informal caregivers to deprescribe (HBQtD)**

framework derived from a systematic literature review, and are aimed at being adequate and relevant to the development and validation of the questionnaire.

Qualtrics is a secure web application that will be used to encode paper questionnaires, and also for data capture from the online questionnaires. Only the users that need to access the data (the research team) will be allowed to do so, and paper questionnaires will be destroyed once they have been transcribed into Qualtrics.

No data transfer is planned in this study, either within or outside the European Union.

In the event of unintended disclosure of data, no negative effects are expected for participants. In addition, any protocol breaches will be immediately (within 7 days) reported by the investigator, in accordance with the investigators, to the Ethical Committee.

The Sponsor or designee must report to ethics committee, serious data breaches : transgressions against the study protocol or the regulation that are likely to significantly affect the safety and rights of a subject or the reliability and robustness of the data generated in the study.

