**4. Validation of the questionnaire – older adult and informal caregiver version**

The final item selection process will incorporate the results of the different qualitative analyses (interviews and FG) and quantitative analyses of the field trial data. This final version of the questionnaire will be then applied to a large sample size of older adults and informal caregiver for reliability validation.

This validity process “... refers to the degree to which evidence and theory support the interpretations of test scores for proposed uses of a test. Validity is, therefore, the most fundamental consideration in developing and evaluating tests” (AERA, APA, & NCME, 2014 cit by Clark & Watson, 2019). As a result, during this phase, a construct validity will be carried out, which is related to the “evaluation of the extent to which a measure assesses the construct it is deemed to measure” (Strauss & Smith, 2009). The internal consistency will be also calculated, as it reflects “the extent to which the questionnaire items are inter-correlated, or whether they are consistent in measurement of the same construct” (Tsang et al., 2017). Finally, a test-retest reliability will be performed, by repeating the administration of the same questionnaire with a small sample of participants (20 older adults and 20 informal caregivers) who have already completed the questionnaire. This process will ensure the consistency of questionnaire items responses across repeated administration (Tsang et al., 2017).

The two additional questionnaires (HLS19\_Q12 and MHLCS) will be administered to all participants (older adults and informal caregivers) in this final stage of the questionnaire validation process.

*Expected duration of subject participation*

Participants will be included throughout the questionnaire development and validation process, which will begin as soon as the ethics committee's opinion is received, and will continue until the sample size required for validation of the questionnaire is reached, in the final phase. The whole process is expected to take around 12 months.

*Planned timetable*

Activities/ Months	2023										2024						
	06	07	08	09	10	11	12	01	02	03	04	05	06	07			
Questionnaire development				15d	15d	15d	15d	15d	15d								
Ethics committee																	
Cognitive pre-test with OA and IC																	
Round with HCP																	
FG with HCP																	
Round with OA and IC																	
FG with OA and IC																	

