The most commonly used estimated of internal consistency is Cronbach’s coefficient alpha ( $\alpha$ ; (McCoach et al., 2013)). Nevertheless,  $\alpha$  is predicted on several assumptions, that are not always respected (Trizano-Hermosilla & Alvarado, 2016; McCoach et al., 2013), which is why the omega coefficient ( $\omega$ ; (McDonald, 1999)) will also be used, as an alternative to  $\alpha$  (Doval, 2023; Trizano-Hermosilla & Alvarado, 2016). In reality, a number of researchers showed that  $\omega$  is a more sensible index, with lower risk of over- or underestimating reliability (Dunn et al., 2014). Therefore, the reliability coefficient range between 0 and 1, and a value above 0.7 will be considered as good internal consistency, while a value above 0.90 will be considered as excellent (Koo & Li, 2016).

According to Koo & Li (2016) “A more desirable measure of reliability should reflect both degree of correlation and agreement between measurements”, that’s why the intraclass correlation coefficient (ICC) will be used to evaluate test-retest reliability at the factor level, and linear-weighted Cohen’s Kappa and percent agreement at the individual item level. These measurements have been used to validate other instruments such as rPATD (E. Reeve et al., 2016) and the rPATD version for BZDs (Péteïn et al., 2023). The ICC classified the reliability

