## 13. ARCHIVING

At the end of the study, the paper data will be stored at the ‘Service des Archives’ from the UCLouvain for as long as dictated by local Ethical Committee and Institutional regulations. Data to be kept at least 20 years after the trial termination according to the Belgian legislation: RD 18 May 2006 art.24

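### Does destroying paper questionnaires after transcription conflict with the archiving section or put the results at risk?

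*Combined protocol and SAP*

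**What the plan says.** Section 9.9 (Data breach, under Quantitative methodology) has paper forms keyed into Qualtrics, after which "paper questionnaires will be destroyed once they have been transcribed into Qualtrics". Transcription is the only stated condition.

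Section 13 (Archiving) says "At the end of the study, the paper data will be stored" in the university archive, for as long as the ethics committee and the institution require. It adds: "Data to be kept at least 20 years after the trial termination". It does not list which paper records it means.

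Three other places bear on the reading:

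- Section 9.3 (recruitment) gives older adults "a stamped envelope for returning the questionnaire and signed consent form", and gives caregivers "a stamped envelope to return the questionnaire and the signed consent form". Signed consent forms are therefore a second kind of paper record.
- Section 9.9 (Qualitative methodology) separately keeps questionnaire comments and focus-group transcripts for 20 years, offline and password-protected.
- Section 9.8 provides an online version for both populations, so only part of the data is keyed from paper. The share is not given.

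Sections 9.8 to 9.10 mention no double entry, source comparison or error limit.

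**The concern.** A completed paper questionnaire is, in ordinary language, paper data. Read that way, section 9.9 destroys what section 13 archives, and staff who follow one section breach the other.

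The statistical worry is that destruction is irreversible. If a value is mis-keyed and the form is gone, it cannot be corrected. The most exposed results are the retest statistics, because section 9.10.2 reports "Kappa and percent agreement at the individual item level" on only 20 people per version. One wrong value there is one of 20 pairs. If it turns an agreeing pair into a disagreeing one, percent agreement for that item falls by 1/20 = 5 points.

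**Working it through.** **1. Can both sections be followed?** The records, side by side:

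| Record | Section 9.9 | Section 13 |
|---|---|---|
| Paper questionnaires, quantitative phase | destroyed after transcription | not named |
| Signed consent forms | no destruction ordered | paper still present at study end |
| Comments and focus-group transcripts | kept 20 years | consistent |
| Qualtrics record | holds the keyed and online answers | can meet the 20-year sentence, which says data, not paper |

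Section 9.9 is a specific rule for one record type. Section 13 is a general rule for what exists at the end of the study. Taking the specific before the general, nothing has to be both destroyed and kept. Only the wider reading of paper data produces a clash.

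**2. How many values could be wrong?** Section 9.1 (Method for data collection) describes a "Second section with 58 questions for older adult questionnaire version and 55 questions for the informal caregiver version" in the initial draft. With 300 validation participants per version (section 9.10.2):

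- 300 × 58 = 17,400 and 300 × 55 = 16,500, together 33,900 values if every form were on paper.
- Assumed low end, 25% paper and 0.1% errors: 33,900 × 0.25 × 0.001 ≈ 8 wrong values.
- Assumed high end, 100% paper and 1% errors: 33,900 × 0.01 = 339 wrong values.

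**3. What does this do to the retest kappa?** The simulation used 20 pairs on the 5-point scale, with 20,000 sets in each of nine scenarios. Latent test-retest correlation was 0.70, 0.85 or 0.92; answers were centred, uniform or skewed. Baseline linear-weighted kappa was 0.44 to 0.72, with a standard deviation across sets of 0.093 to 0.147.

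One mis-keyed value in a random pair:

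| | Adjacent category | Random wrong category |
|---|---|---|
| Mean fall in kappa | 0.009 to 0.030 | 0.030 to 0.067 |
| Sets in which kappa rises | 18 to 38% | 11 to 28% |
| Mean fall in percent agreement (points) | 0.8 to 2.7 | 1.3 to 3.2 |

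The average fall in agreement is below 5 points because only 40 to 71% of pairs agree to begin with.

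Every value mis-keyed independently at rate e, all retest forms on paper:

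| e | Adjacent category | Random wrong category |
|---|---|---|
| 0.1% | 0.0004 to 0.0012 | 0.0012 to 0.0027 |
| 0.5% | 0.0017 to 0.0061 | 0.0058 to 0.0134 |
| 1% | 0.0033 to 0.0118 | 0.0117 to 0.0263 |

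Cross-check: an item has 2 × 20 = 40 retest values, so 1% gives 0.4 expected errors, and 0.4 × 0.067 ≈ 0.027, in line with 0.0263. Even the largest mean fall set against the smallest standard deviation is 0.0263 / 0.093 ≈ 0.28. With half the forms on paper the fall is about half; with none it is zero.

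**4. And the factor analysis?** Suppose answers are uniform on five categories and a mis-keyed value is any wrong category with equal chance. Its expected value given the true answer x is (15 − x)/4, a slope of −1/4. The correlation between true and keyed answers is then (1 − e) − e/4 = 1 − 1.25e. At e = 1% this is 0.9875, and a loading at the plan's 0.30 cut-off becomes 0.30 × 0.9875 ≈ 0.296. Uneven answers attenuate a little more.

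**5. And the logistic regression?** The willingness and current-deprescribing questions in section 1 of the questionnaire appear to supply its outcomes. At 1% errors and all paper, 300 × 0.01 = 3 forms per version would carry a wrong value on one such question.

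**The case for a change.** The best case for a change is that the loss is irreversible and the remedy cheap. Section 9.9 makes transcription the sole trigger, section 13 exempts nothing, and the protocol itself treats threats to the reliability of the data as reportable to the ethics committee. A sentence defining the archived paper, plus a check of at most 40 retest forms per version (40 × 58 = 2,320 or 40 × 55 = 2,200 values), would settle it.

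Two parts stand: the term is undefined, and no check is described. The rest is weaker.

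- Silence on data-entry checks is not a plan to omit them. Comparing entries with paper before discarding it fits within the wording.
- The check is not as cheap as it looks. Those counts omit the section 1 questions and the health literacy and locus-of-control questionnaires, which all validation participants complete. Retest participants are also people who have already completed the questionnaire, so their first forms may be gone when they are selected. Checking those forms would mean delaying destruction or checking every form.
- Keeping the paper instead would reverse a defensible privacy choice, since the questionnaire and the signed consent form come back in the same envelope.
- Archiving is tied to ethics committee and institutional rules that are not among the documents. They may already settle which paper is kept.

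**Conclusion.** No change is needed. Sections 9.9 and 13 are loosely worded but compatible, and the unmentioned data-entry check is ordinary practice that the text leaves room for. A definition of paper data would help readers but would not alter any analysis.

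The mean kappa loss is at most 0.026 in the worst case modelled, against sampling variation of 0.09 to 0.15. The kappa bands in section 9.10.2 only describe strength of agreement, so no item or factor is kept or dropped on them. A loading at the cut-off moves by about 0.004 under uniform answers.

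This rests on assumed keying error rates of 0.1 to 1%, assumed answer distributions and an unknown paper share. It also takes errors to be independent. A systematic fault, such as a reversed scale or a shifted column, is not covered by these figures.
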